## IV. Synopsis

Study Title	Efficacy, safety and pharmacokinetics of ascending dosages of moxidectin alone and in comparison to ivermectin against Strongyloides stercoralis infection in adults: a randomized controlled trial	
Study Type	Phase 2 trials – Phase 2a (trial A) & Phase 2b/3 (trial B)	
Sample size	210 (trial A) and 350 (trial B) in two settings	
Indication	Strongyloidiasis stercoralis infection (larvae in stool)	
Investigational Product and Reference Treatment	Investigational product: moxidectin Reference treatment: ivermectin	
Protocol Number, Date and Version	2, 01.07.2020, v2.2	
Trial registration	Will be registered on ( http://www.controlled-trials.com/ )	
Study Rationale	
 
To provide evidence on:
 
(A) Effective doses and safety of moxidectin in adults against infection with S. stercoralis in Laos (trial A: dose finding study).
 
(B) Efficacy and safety of moxidectin compared to ivermectin in adults against infection with S. stercoralis in Laos and Cambodia (trial B: parallel group study).
 
	
Study Objectives	
 
To determine the efficacy and safety of:
 
a) seven ascending oral moxidectin dosages in adults infected with S. stercoralis, namely placebo, 2 mg, 4 mg, 6 mg, 8 mg, 10 mg, 12 mg and to measure moxidectin disposition in adults using a microsampling device.
 
b) the recommended dose moxidectin (i.e. the most promising dosage identified in trial A; 8 mg) in comparison to the standard treatment dose of ivermectin (200 μg/kg) in adults infected with S. stercoralis.
 
Our primary objective is to determine the dose-response of
 
	
	
 
moxidectin based on cure rates (CR) against S. stercoralis and to quantify the efficacy of the recommended dose to the standard treatment (ivermectin) in adults:
 
a) in a dose finding study
 
placebo, 2 mg, 4 mg, 6 mg, 8 mg, 10 mg and 12 mg moxidectin
 
b) in a parallel group trial
 
	

	1	
	8 mg moxidectin (absolute value depends on results of (A)), and 200 $\mu$ g/kg ivermectin.	
	The secondary objectives of the trial are:	
	
 
to evaluate the safety and tolerability of the dose- dependent treatment regimes.
 
	
	
 
to evaluate the safety and tolerability of moxidectin compared to ivermectin.
 
	
	
 
to compare the larvae reduction rate (LRR) of the different treatment regimens against S. stercoralis (trial A and B).
 
	
	
 
4) trial A: to determine an exposure- (including Cmax, AUC and tmax) -response correlation of moxidectin in adults.
 
	
	
 
trial A: to compare the exposure-response of moxidectin using venous and capillary blood.
 
	
	
 
6) to evaluate the cure rate of the different moxidectin treatment regimens against co-infection.
 
	
	7) trial A: to determine the population PK parameters of the optimal dose of moxidectin in the treatment of S. stercoralis.	
	
 
8) trial B: to relate socioeconomic characteristics (possession of indicator assets), access to sanitation, water facilities, and hygiene and environmental reservoirs behaviour to infection intensity
 
	
Study design	Single blinded, randomized controlled trial (trial A) (participants and lab technicians are blinded); double blinded randomized controlled non-inferiority trial (trial B)	
Study product / intervention	Administration of a single oral dose of moxidectin or ivermectin	
Comparator(s)	Matching placebo (trial A, B), Ivermectin (trial B)	
Key inclusion / Exclusion criteria	Inclusion: Adults ( $\geq$ 18, <65 years) infected with S. stercoralis , absence of major systemic illnesses, written informed consent signed by individual	
	Exclusion: Any abnormal medical conditions or chronic disease, negative diagnostic result for S. stercoralis , no written informed consent by individual. Pregnant women, lactating women or women planning to become pregnant within the next six months	
Primary Endpoints	CR on S. stercoralis	
Secondary Endpoints	LRR against S. stercoralis , safety and pharmacokinetic parameters in S. stercoralis infected populations	

Exploratory Endpoints	Co-infection
Interim Analyses	None
Study Duration	8 weeks (trial A) / 8 weeks (trial B)
Schedule	08/2019 of first-participant in (planned) 08/2021 of last-participant out (planned)
Measurements & procedures	Three stool samples will be collected at baseline if possible on three consecutive days or otherwise within a total maximum of 6 days and analysed by a quantitative Baermann method (in duplicates) for S. stercoralis infection. Co-infection with T. trichiura, A. lumbricoides and hookworm infection will be identified using duplicate Kato-Katz thick smears on stool samples from two consecutive days. The medical history of the participants will be assessed with a standardized questionnaire, in addition to a clinical and physical examination carried out by the study physician shortly before treatment day. The adults will also be interviewed before treatment, 3 and 24 hours as well as 28 days after treatment about the occurrence of AEs. The efficacy of the treatment will be determined 21-28 days post-treatment by collecting another three stool samples. All stool samples will be examined with duplicate Baermann assays and Kato-Katz thick smears and recorded quantitatively. A subsample of adults will further be sampled using finger pricking for micro sampling at 0, 2, 4, 8, 24, and 72 hours, 7 and 28 days post treatment to evaluate pharmacokinetic parameters (trial A). For validation of the analytical method the subsample of one study arm (8 mg, trial A) will undergo venous blood sampling in addition to finger pricking. To all participating households, a brief questionnaire will be administered assessing information on socioeconomic characteristics (possession of indicator assets) and access to sanitation, water facilities, and hygiene behaviour at first visit. Additionally, soil and water samples at different sites will be taken.
Statistical Analyses	An available case analysis (full analysis set according to the intention to treat principle) will be performed, including all subjects with primary end point data. Supplementary, a per-protocol analysis will be conducted. CRs will be calculated as the percentage of larvae-positive subjects at baseline who become larvae-negative after treatment. Larvae per gram (LPG) stool sample will be assessed by calculating the mean of the larvae counts from the three duplicate Baermann assays and divided by the mean weighted amount of these stool samples. The LRR will

relation to	the	drugs.
investigated drugs		

#### V. Abbreviations

AE	Adverse event
AUC	Area under the curve
CI	Confidence interval
CR	Cure rate
CRF	Case report form
DALYs	Disability-adjusted life years
DBS	Dried blood spot
DF	Dose finding
DSMB	Data and safety monitoring board
EKNZ	Ethikkommission Nordwest- und Zentralschweiz
GCP	Good clinical practice
Hb	Hemoglobin
ICH	International council for harmonization of technical requirements for
	pharmaceuticals for human use
IEC	Independent ethics committee
LC-MS/MS	Liquid chromatography tandem mass spectrometry
LPG	Larvae per gram
LRR	Larvae reduction rate
NLME	Nonlinear mixed-effects
NTD	Neglected tropical disease
PI	Principal investigator
PK	Pharmacokinetics
SAE	Serious adverse event
WHO	World Health Organization

# 2. Background information

Over the last decade, increasing evidence has linked major neglected tropical diseases (NTDs) to significant adverse impacts on human and economic development. NTDs affect more than one billion people globally, in particular poor, and marginalized tropical populations, and contribute to an estimated 3.3 million disability-adjusted life years (DALY) lost globally. NTD also includes soil-transmitted helminthiasis such as strongyloidiasis covered in this clinical study [1].

*Strongyloides stercoralis* is a soil-transmitted nematode found almost worldwide, though with largest prevalence in tropical and subtropical regions, as an example Lao PDR [2-4], and belongs to the most neglected infections among the NTDs.

Infectious larvae are found in humid soil that is contaminated with feces. Upon penetration of the intact skin of their host, *S. stercoralis* can reproduce within their human host. This endogenous autoinfection may result in long-lasting infections, which is not seen in other soil-transmitted helminth infections. Furthermore, *S. stercoralis* is known for its unique and threatening feature to cause systemic infection. Not surprisingly, without appropriate therapy, thus infections do not resolve and may persist for life. In case of immunodeficiency the infections are severe if not even life-threatening. However, most infections, chronic low-intensity infections, in particular, remain non-specific and might be expressed as suffering from malnutrition, physical and cognitive retardation, and reduced work performance [5]. *S. stercoralis* infections are typically most intense and debilitating in adults causing significant morbidity [6-8].

Today, chemotherapy combined with health education programs, remain the core to reduce the serious health impacts. The currently advocated treatments by the World Health Organization (WHO) are a single dose of ivermectin or multiple doses of albendazole, which has a lower efficacy compared to ivermectin [9, 10]. Since drug resistance is a threat and the drug pressure is high it is of uttermost importance to develop new treatment alternatives. Among new candidates in the human anthelminthic drug development pipeline, moxidectin, a macrocyclic lactone might be an excellent alternative. Moxidectin has been approved recently by the Food and Drug Administration (FDA) for use against onchocerciasis. (http://www.who.int/tdr/news/2018/moxidectin-approved-as-treatment-for-river-blindness/en/) [11]. The drug offers some advantages over ivermectin. First of all, moxidectin is used weight independent (for onchocerciasis at an 8 mg fixed dose), which renders the administration easier to handle, especially when treating large communities. Second, moxidectin has been shown to have a lower neurotoxic potential than ivermectin [12]. Thirdly, the pharmacokinetic profile of moxidectin in healthy individuals (very long  $t_{1/2}$ , and a large Vd/F, compared to ivermectin) arises prospects for efficacy also against long-term parasitic activity – as is particularly important when treatment of *S. stercoralis* is desired [13]. Finally, most importantly moxidectin has been used successfully in veterinary medicine against ivermectin-resistant strains [14].

The clinical significant adverse advents of moxidectin are though very similar to those of ivermectin and a consequence of excessive concentration. The drug is typically used as a single oral dose (8 mg) in patients aged 12 years and older and evaluated as an extremely safe drug. Most common side effects include hypotension, itching, headache, abdominal pain, fever, dizziness or diarrhea. Serious or even fatal encephalopathy may occur in patients coinfected with Loa Loa. Furthermore, moxidectin is known to worsen onchodermatitis in patients with hyperactive onchodermatitits. Laos and Cambodia are not endemic neither for Loa Loa nor onchodermatitits and thus these symptomatic advents shall not constitute a risk in our study. Nevertheless patients with symptoms for onchodermatitits (severe itching, bumps under the skin, blindness) will be excluded from the study. Additionally, although conclusive teratogenic data on moxidectin are missing, decreased fetal survival and increased fetal born with malfunctions is observed in some animals studies. Thus we do not see it recommended using moxidectin with pregnant female and pregnant patients will strictly be excluded. Last, owing to the lipophilic nature of moxidectin, extraction of moxidectin to the breast milk of nursing mothers is very likely and could be demonstrated in lactating cows. The risk of moxidectin in nursing infants is though unknown. Breastfeeding females will be excluded in this study.

In a small exploratory study using the veterinary formulation, a single dose of 8 mg of moxidectin, and a small sample size (127 participants) moxidectin has been found to be efficacious against *S. stercoralis* (cure rates of 93.7%) and its tolerability confirmed also in patients [15].

Yet, despite the attractive attributes of moxidectin and its promising potential in the treatment of *S. stercoralis* it remains off-label. First of all, the efficacy of the human formulation against *S. stercoralis* infections has not been assessed to date, neither has the optimal dosage been elucidated. A single dose of 36 mg moxidectin in healthy adults was the highest single dose tested to date that still represented a well-tolerated dose [13]. The 12 mg, therefore, selected as the highest dose in our study to elaborate a dose-response relationship for the use of moxidectin in *S. stercoralis* infections will not pose any health risk.

Second, to date pharmacokinetic studies of moxidectin have been conducted exclusively in a low number of healthy adults and consequently the pharmacodynamic behavior of moxidectin is completely unknown. [13, 16]. Yet, a PK characterization is central to understand the human body's response to a drug, especially in populations that physiologically differ from healthy adults. Physiological abnormalities like mal- or undernutrition and intestinal worms, such as *S. stercoralis*, can potentially affect the PK of a drug [17, 18]. Being minimal invasive, minimal painful, simple and rapidly performed, micro-blood sampling (e.g. the dried blood spot (DBS)) has developed into the method of choice for PK studies and will be also used in this study. Micro-blood sampling has been repeatedly proven to correlate well with the standard method that uses venous blood [19-22]. Micro blood sampling analysis has not been used to measure moxidectin blood levels and, therefore, requires a validation. For this purpose, a formal validation, using blood samples from two vascular sides, will be performed in parallel; supporting and confirming the linearity between venous and capillary blood also for moxidectin.

Last, it would be crucial to elucidate if moxidectin at an appropriate dose could serve as an alternative to ivermectin, which is to date one of the very few but the drug of choice against *S. stercoralis.* 

In view of remaining knowledge gaps of the optimal doses of moxidectin against *S. stercoralis* as well as insufficient evidence on safety and efficacy parameters our study aims in a first step to thoroughly investigate the efficacy and safety of ascending doses of moxidectin (2 mg, 4 mg, 6 mg, 8 mg, 10 mg, 12 mg versus placebo) against *S. stercoralis* infection, complemented by PK studies. Once the optimal dose of moxidectin has been identified in this phase 2a trial (trial A: DF study), we aim in a second study to compare the safety and efficacy of the single best dose of moxidectin to the standard dose of ivermectin in two phase 2b trial settings (trial B: parallel group study). This study will be complemented by assessing socioeconomic factors, household characteristics and behaviors, using a household questionnaire. Moreover, we will inform about potential environmental risk factors.

# 3. Trial objective and purpose

#### The primary study objectives are

- (A) To determine the nature of the dose-response (efficacy in terms of cure rate) using oral moxidectin dosages: 2 mg, 4 mg, 6 mg, 8 mg, 10 mg, 12 mg and placebo in a total of 210 adults infected with *S. stercoralis* (trial A: DF study).
- (B) To determine if the efficacy in terms of cure rate of an oral single optimal dose of moxidectin (8 mg based on the outcome of (A)) is non-inferior to the standard dose of a single oral ivermectin application (200 μg/kg), in 350 infected adults in two settings. The non-inferiority margin is set to 10%-points (trial B: parallel group study).

#### The secondary study objectives are

- 1.) To compare the efficacy based on larvae reduction rates of ascending oral moxidectin dosages in a total of 210 adults infected with *S. stercoralis*.
- 2.) To determine safety & tolerability of ascending oral moxidectin dosages in a total of 210 adults infected with *S. stercoralis*.
- 3.) To comparatively assess the efficacy based on larvae reduction rates moxidectin versus ivermectin (200 μg/kg), the current drug of choice, against *S. stercoralis* in 350 adults infected with *S. stercoralis*.
- 4.) To determine safety & tolerability of moxidectin versus ivermectin (200 μg/kg), the current drug of choice, against *S. stercoralis* in 350 adults in two countries infected with *S. stercoralis*.
- 5.) To determine pharmacokinetic parameters in 10 adults infected with *S. stercoralis*, after oral moxidectin administration of 8 mg, using venous as well as capillary blood allowing the validation of the micro sampling analysis to measure moxidectin blood levels.
- 6.) To measure moxidectin deposition and determine exposure (including Cmax, AUC and tmax)response correlation using a microsampling technology after oral moxidectin administration of 2 mg, 4 mg, 6 mg, 8 mg, 10 mg, 12 mg versus placebo in a total of 90 adults infected with *S. stercoralis*.
- 7.) To determine the population PK parameters of the optimal dose of moxidectin in the treatment of *S. stercoralis.*

# 4. Methodology

## 4.1. Primary and secondary endpoint

CR (i.e. conversion from being larvae positive pre-treatment to larvae negative post-treatment) is the primary endpoint. In addition, LRR and key PK parameters will be determined and safety & tolerability of treatment evaluated (secondary end points). CRs against co-infections are considered as exploratory endpoints.

## 4.2. Type of trial

Single blinded, randomized placebo-controlled, dose-ranging trial (trial A: DF study) (participants and lab technicians are blinded).

[figure not shown]
Double blinded, randomized, non-inferiority trial (trial B: parallel group study).

The PK sub-studies of trial A and trial B are single blinded.

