## 4.3. Trial design

Two randomized-controlled trials will be conducted; a dose-ranging study (trial A) and a parallel group study (trial B), with seven and three treatment arms, respectively to be followed-up each over a 21-28 days period. The second comparative trial will be conducted as a non-inferior study with a non-inferiority margin of 10%-points.

- (A) The DF study (Figure 1, top) is designed as a seven-armed trial including arms with ascending dose administration of moxidectin: 2 mg, 4 mg, 6 mg, 8 mg, 10 mg, 12 mg and a placebo-arm.
- (B) The parallel group study (Figure 1, bottom) is designed as a two-armed trial including one arm with a single drug administration of a standard dose of ivermectin (200  $\mu$ g/kg) and one arm with a treatment of a single best dose of moxidectin (8 mg, according to the findings in (A)). The optimal dose of findings in (A) are evaluated as the dose that is high enough to demonstrate efficacy in the target population, yet low enough to minimize safety concerns and adverse events.

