#### 5.4. Treatment of subjects

2 mg tablets of moxidectin will be obtained from Medicines Development for Global Health (MDGH), Australia. Ivermectin (3 mg) will be purchased from Merck, Switzerland. Matching placebo tablets (moxidectin and ivermectin) will be obtained from the Medicines Development for Global Health (moxidectin) and produced and a certificate of manufacture and analysis provided by the University of Basel (ivermectin). The appropriate doses will be calculated and the correct amount of moxidectin and placebo (trial A) and moxidectin, moxidecin placebo or ivermectin or ivermectin placebo tablets (trial B) will be administered to all participants. Due to blinding the tablets will be repacked into neutral separate opaque plastic bags each containing the adequate dose of moxidectin tablets and/or placebo tablets (trial A). In trial B, the tablets will be handed out from the drug container according to the randomization list. Each person will receive (i) either 4 moxidectin or 4 moxidecin placebo tablets and (ii) the number of ivermectin tablets with regard to their weight category or the corresponding number of ivermectin placebo tablets. The tablets will as long as applicable be stored in the original package and at any time (except treatment day) be stored according to manufacture prescription, sealed and away from light.

The principal investigator(s) or co-investigator(s) is responsible for drug accountability at the study site. Maintaining drug accountability includes careful and systematic study drug storage, handling, dispensing and documentation of administration.

Treatment and blood sampling (capillary blood sampling for a total of 90 participants, in trial A and venous blood sampling for 10 patients (trial A)) will be done community-based in local temples, that are quiet and spacious locations, where people like to gather and organize meetings. Infrastructure as required for the study needs (i.e tables, chairs, a fridge, a cover from rain and sun) will be installed as necessary at the specific study days. Opportunities

(approximately three daybeds) will be provided to comfortably withdraw the venous blood (4 samples on day 1 and 4 samples within the next 28 days) and to provide a possibility to lie down in case of an arising unwell feeling. Participants will receive a breakfast two hours prior to treatment as well as lunch during the day once absorption of the drug is complete.

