# 6. Assessment of safety

### 6.1. Adverse event definition

Few adverse events have been reported following moxidectin or ivermectin administration in STH-infected individuals. The most common AEs were abdominal cramps, headache, nausea, diarrhea, fever and vertigo [11, 12, 36, 37].

The observation time for AE starts when the treatment is initiated. Subjects will be kept for observation for at least 3 hours following treatment for any acute AEs. If there is any abnormal finding, the local study physician will perform a full clinical examination and findings will be recorded. An emergency kit will be available on site to treat any medical conditions that warrant urgent medical intervention. Participants will also be interviewed 3, 24 hours, 28 days after treatment about the occurrence of AEs.

Information on all AE (incidence, onset, cessation, duration, intensity, frequency, seriousness and causality) will be entered immediately in the source document, and also in the appropriate AE module of the case report form. For all AEs, sufficient information will be pursued and/or obtained so as to permit i) an adequate determination of the outcome of the event (i.e. whether the event should be classified as a SAE); and; ii) an assessment of the casual relationship between the AE and the study treatments. Intensity of AE will be judged by the study physician, following guidelines by the European Medicine Agency (Note for Guidance on Clinical Safety Data Management).

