#### 6.1.2. Severity grading

Adverse signs or symptoms will be graded by the investigator as mild, moderate, severe or life threatening according to the following definitions (https://evs.nci.nih.gov/ftp1/CTCAE/CTCAE 4.03 2010-06-14 QuickReference 5x7.pdf).

Grade	Definition
1:	mild adverse events
2:	moderate adverse events.
3:	severe adverse events.
4:	life threatening or disabling adverse events.
5:	death related to adverse events.

The observation time for adverse events starts when the treatment is initiated and continues until 28 days post-treatment. For the purpose of this trial, disease progression and relapse will be considered as treatment failure, not as an AE.

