#### 6.1.3. Relatedness

Relatedness will be assessed as defined below based on the temporal relationship between the AE and the treatment, known side effects of treatment, medical history, concomitant medication, course of the underlying disease and trial procedures.

Possibly related: an AE which can medically (pharmacologically/clinically) be attributed to the study treatment.

Unrelated: an adverse even which is not reasonably related to the study treatment. A reasonable alternative explanation must be available.

An AE that is determined to be related to the administration of a study product is referred to as an "adverse drug reaction."

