#### 6.2. Methods of recording and assessing adverse events

Patients will be kept for observation for at least 3 hours following each morning treatment for any acute AEs. During the reporting period, any unfavorable changes in the subject's condition will be recorded as adverse events, whether reported by the subject or observed by the investigator. In case of any abnormal finding, the local study physician will perform a full clinical examination and findings will be recorded. An emergency kit will be available on site to treat any medical conditions that warrant urgent medical intervention.

In addition, patients will be also interviewed by a nurse and/or a physician about the occurrence of AEs 24 hours after treatment.

Information on all AEs (onset, duration, intensity, seriousness and causality) will be immediately entered in the appropriate AE module of the CRF which is considered as a source document. For all AEs, sufficient information will be pursued and/or obtained so as to permit i) an adequate determination of the seriousness of the event (i.e. whether the event should be classified as a SAE); ii) an assessment of the casual relationship between the AE and the study treatments (i.e. whether the event should be classified as an adverse drug reaction); and iii) an assessment of intensity of AEs by the study physician.

All SAE, unexpected adverse drug reactions, or SUSARs must be reported as described in Section 6.3.

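### Trial A's stated blind leaves out everyone who elicits, grades or attributes adverse events, although those events are part of the criterion for choosing the dose

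*Combined protocol and SAP*

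**What the plan says.** All references are to the combined protocol and SAP.

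- **Who is blinded.** Section 4.2 calls trial A a "Single blinded, randomized placebo-controlled, dose-ranging trial (trial A: DF study) (participants and lab technicians are blinded". The synopsis repeats the list and sets it against the second trial: "participants and lab technicians are blinded); double blinded randomized controlled non-inferiority trial (trial B".
- **Who interviews.** Section 6.2 has a nurse and/or a physician ask about AEs at 24 hours. Sections 4.3.3 and 6.1 also schedule interviews at 3 hours and day 28 without naming the interviewer.
- **Who grades.** Section 6.1 states "Intensity of AE will be judged by the study physician", and section 6.2 again refers to "an assessment of intensity of AEs by the study physician". Section 6.1.2 gives the task to someone else: "Adverse signs or symptoms will be graded by the investigator as mild, moderate, severe or life threatening".
- **Who attributes.** Section 6.1.3 says "Relatedness will be assessed as defined below based on the temporal relationship between the AE and the treatment, known side effects of treatment", among other factors. It names no assessor.
- **What the AEs are used for.** Safety and tolerability are secondary endpoints (section 4.1). Section 4.3 defines the optimal dose as one high enough to show efficacy, "yet low enough to minimize safety concerns and adverse events".
- **How they are analysed.** Section 7.3 plans a descriptive comparison of the proportions reporting AEs before and after treatment.
- **How allocation is concealed.** Section 4.4 keeps the codes locked at the Swiss institute, with a sealed emergency copy held by a co-investigator, and keeps the blind until the data are verified. Section 5.4 says that in trial A "the tablets will be repacked into neutral separate opaque plastic bags".

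**The concern.** Blinding the laboratory protects cure rate and larvae reduction rate. It does nothing for safety, which comes from interviews about symptoms such as headache, itching, nausea and abdominal pain. How often these are recorded depends partly on how the questions are put and followed up.

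The protocol also gives an interviewer a reason to expect a trend, since section 2 links clinically significant adverse events of moxidectin to excessive concentration. An interviewer who knew that one participant had placebo and another the top dose could, without intending it, create or hide a dose trend in AEs. That trend is one of the two considerations in the choice of the trial B dose. AEs are compared only descriptively and there is no data and safety monitoring board (section 11.2), so the plan describes no independent check that would reveal such a bias.

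**Working it through.** The plan gives no figure for this point, so the check is mainly a comparison of sections.

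**Step 1. Match each AE task to the blinded list (sections 4.2 and synopsis).**

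| Task in trial A | Assigned to | Section | On the blinded list? |
|---|---|---|---|
| AE interview, 24 h | nurse and/or physician | 6.2 | no |
| AE interview, 3 h and day 28 | not named | 4.3.3, 6.1 | cannot tell |
| Intensity | study physician | 6.1, 6.2 | no |
| Severity grade | investigator | 6.1.2 | no |
| Relatedness | not named | 6.1.3 | cannot tell |
| Stool microscopy (cure rate) | laboratory technicians | 4.3.1 | yes |

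No AE task is assigned to a role that the plan declares blinded. Sections 6.1 and 6.2 also differ from 6.1.2 on who grades.

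**Step 2. Ask whether the concealment measures close the gap.** Section 4.4 does not say whose blind is kept. Section 5.4 places the physician, with an investigator or co-investigator, at dosing. Tablets contain 2 mg, so the active tablets per participant run from 2/2 = 1 to 12/2 = 6. The bags may also hold placebo tablets, but no section says that every bag has the same count. These measures limit casual unblinding; they do not declare the AE assessors blind.

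**Step 3. Look for other clues to the dose.** Venous sampling takes place only in the 8 mg arm, in 10 people (section 4.3.5). Capillary sampling covers at most 15 per arm and 90 in total; 90/15 = 6, which fits the six active arms, whereas seven arms would give 7 × 15 = 105. Objective 6 in section 3 also mentions placebo within the 90, so it is not settled that placebo is left out.

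**Step 4. Trace each kind of bias to an output.** The measure in section 7.3 counts whether a participant reports an AE. Uneven eliciting can move it. Changing a grade or an attribution cannot; those changes would show only in summaries of intensity or relatedness.

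**Step 5. Illustrate the scale.** Inputs: 30 per arm (section 7.2). Assumptions not in the documents: three participants elicited differently, and an AE proportion p equal in two arms.

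- Shift in one arm: 3/30 = 0.10, or 10 percentage points.
- Standard error of a between-arm difference in post-treatment proportions: √(2p(1−p)/30).
- p = 0.10: √(2 × 0.10 × 0.90/30) = 0.077.
- p = 0.20: √(2 × 0.20 × 0.80/30) = 0.103.
- p = 0.40: √(2 × 0.40 × 0.60/30) = 0.126.

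A 10-point shift is therefore about 0.8 to 1.3 standard errors over this range. The standard error of the before-and-after difference would also need the within-person correlation, which the documents do not give.

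**The case against.** Five points can be made against this.

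1. **The assessors may well be blind in practice.** Locked codes, a sealed copy for emergencies and opaque bags all restrict access to allocation, and no section says that the physician knows the dose. This stands. A reader might infer from the single-blind label that the assessors do know the dose, but the documents support only that they are not declared blind. If they are in fact blind, the plan should say so.
2. **Relatedness is not assigned to the physician.** This also stands. It is tempting to read the physician's role as covering causality, but sections 6.1 and 6.2 give that role intensity only. Nor does a reference to known side effects require knowledge of the dose.
3. **Participants are blinded and a standardized symptom questionnaire is used** (footnote f to Table 1). This reduces the room for uneven probing. It does not remove it, because participants are also examined and other symptoms can be recorded.
4. **The effect on dose choice may be small.** Cure rate is read blind, the dose criterion is qualitative with no AE threshold, and section 2 reports that 36 mg, three times the top dose here, was tolerated. A reader might infer that 8 mg was chosen on biased safety data; nothing in the documents shows that AEs drove the choice.
5. **The change may come too late.** Protocol version 2.2 is dated 01.07.2020, the first participant was planned for 08/2019, and sections 3 and 4.3 already attribute 8 mg to trial A. Yet the synopsis still says that the value depends on trial A, and trial A is described in the future tense. Completion is likely but not established, so the remedy must cover both cases.

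**Conclusion.** The point holds as a gap in trial A's stated blind and a low-cost improvement. It is not a threat to the primary endpoint and does not concern trial B, which is labelled double blinded. The AE interviewers and graders named in the plan are outside the blinded list, relatedness has no named assessor, and nothing in the design requires any of them to know the dose.

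The main exposure is the planned AE proportion, through uneven eliciting. The 10-point figure shows that a few participants matter with 30 per arm; it does not predict a bias, and it should not be read as the effect of regrading, which leaves the planned proportion unchanged. The conclusion rests on reading the list in section 4.2 and the synopsis as complete, which the single-blind label supports but the text does not say outright.

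**What to change.** **If AE collection in trial A is still open:**

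- Amend section 4.2 and the synopsis so that the AE interviewers at 3 hours, 24 hours and day 28, the grading physician or investigator, and a named relatedness assessor are also blinded to allocation in trial A.
- State in section 5.4 that all trial A bags hold the same number of tablets and are filled by someone who takes no part in AE assessment.
- Require intensity and relatedness to be recorded before the codes are released.
- Where blood sampling could reveal the arm, use AE interviewers who were not present at sampling, as far as staffing allows.

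**In either case:** reconcile sections 6.1 and 6.2 with 6.1.2 on who grades.

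**If the trial A AE data are already collected:** document which AE interviewers and assessors had access to allocation, and qualify the between-dose AE comparisons, and their part in the dose choice, accordingly.

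**Cost:** protocol wording and separation of roles among existing staff. Matching placebo, opaque bags and a sealed emergency code are already planned. The blind would remain imperfect for pharmacokinetic participants, above all the 10 with venous sampling in the 8 mg arm, and a blinded physician would have to request the code in an emergency.
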